## **7.2. Laboratory Evaluations**

Laboratory data collected during the study will be analyzed and summarized using both quantitative and qualitative methods. Summaries of laboratory data will be provided for the Safety Analysis Set and will include all available data.

The analysis will be based on values reported in conventional units. When values are below the LOQ, they will be listed as such, and the closest imputed value will be used for the purpose of calculating summary statistics as specified in Section 3.7. Hemolyzed test results will not be included in the analysis, but they will be listed in by-subject laboratory listings.

A by-subject listing for laboratory test results will be provided by subject ID number and visit in chronological order for hematology, serum chemistry, and urinalysis separately. Values falling outside of the relevant reference range and/or having a severity grade of 1 or higher on the Gilead Grading Scale for Severity of Adverse Events and Laboratory Abnormalities will be flagged in the data listings, as appropriate.

No inferential statistics will be generated.

### **7.2.1. Summaries of On Treatment Numeric Laboratory Results**

Descriptive statistics (n, mean, SD, median, Q1, Q3, minimum, and maximum) will be provided using all available data by treatment group for chemistry (including alanine aminotransferase [ALT], albumin, alkaline phosphatase [ALP], aspartate aminotransferase [AST], creatine kinase, fasting glucose, total bilirubin, fasting total cholesterol, lactate dehydrogenase [LDH]), hematology (including hemoglobin, lymphocytes, neutrophils, white blood cells and platelets), and estimated creatinine clearance calculated by the Cockcroft-Gault method as follows:

- Baseline values
- Values at each postbaseline visit
- Change from baseline at each postbaseline visit

A baseline laboratory value will be defined as the last measurement obtained on or prior to the date/time of first dose of any study drug. Change from baseline to a postbaseline visit will be defined as the visit value minus the baseline value. The mean, median, Q1, Q3, minimum, and maximum will be displayed to the reported number of digits; SD values will be displayed to the reported number of digits plus 1.

Median (Q1, Q3) of the observed values for albumin, ALT, ALP, lipase, estimated creatinine clearance, total bilirubin, triglycerides, total cholesterol, hemoglobin, lymphocytes, neutrophils, platelets, and white blood cells will be plotted using a line plot by treatment group and visit. In the case of multiple values in an analysis window, data will be selected for analysis as described in Section 3.8.3.

### **7.2.2. Summaries of Numeric Laboratory Results during TFFU Period**

Descriptive statistics (n, mean, SD, median, Q1, Q3, minimum, and maximum) will be provided using all available data for chemistry (including albumin, ALT, ALP, AST, total bilirubin, creatine kinase, fasting glucose, fasting total cholesterol and LDH), hematology (including hemoglobin, lymphocytes, neutrophils, white blood cells and platelets), and estimated creatinine clearance calculated by the Cockcroft-Gault method as follows:

- Baseline values
- Value at last on-treatment visit (TFFU baseline)
- Values at each TFFU visit
- Change from TFFU baseline at each TFFU visit

Last on-treatment laboratory value (TFFU baseline) is defined as the last measurement obtained on or prior to the date/time of last dose of any study drug including GS-9992, TAF and NUC treatment. Change from TFFU baseline value to a post treatment visit will be defined as the visit value minus the last on-treatment value. The mean, median, Q1, Q3, minimum, and maximum will be displayed to the reported number of digits; SD values will be displayed to the reported number of digits plus 1.

Mean  $\pm$  SD of the observed values for total bilirubin will be plotted using a line plot by HBeAg status and treatment group and visit. In the case of multiple values in an analysis window, data will be selected for analysis as described in Section 3.8.3.

### **7.2.3. Graded Laboratory Values**

The Gilead Grading Scale for Severity of Adverse Events and Laboratory Abnormalities will be used to assign toxicity grades (0 to 4) to laboratory results for analysis. Grade 0 includes all values that do not meet the criteria for an abnormality of at least Grade 1. For laboratory tests with criteria for both increased and decreased levels, analyses for each direction (ie, increased, decreased) will be presented separately.

### 7.2.3.1. Treatment-Emergent Laboratory Abnormalities

TE laboratory abnormalities are defined as values that increase at least 1 toxicity grade from baseline at any postbaseline time point, up to and including the cutoff day defined as follows:

#### For the **Analysis for 12 Week Regimen**:

- For subjects treated with GS-9992 and TAF or commercially available NUC(s) (ie, Group 1, 3 -5):

30 days after permanent discontinuation of GS-9992

- For subjects treated with TAF only (ie, Group 2):

For those who remained on TAF treatment for the first 12 weeks plus 30 days (ie, from Day 1 to Day 114):

- 30 days after the first 12 weeks treatment of TAF (ie, no later than Day 114)

For those who prematurely discontinued TAF during the first 12 weeks plus 30 days (ie, from Day 1 to Day 114):

- 3 days after permanent discontinuation of TAF or up to Day 114, whichever comes earlier

#### For the **Analysis for 48 Week Regimen**:

- For subjects treated with GS-9992 and TAF (ie, Group 1, 3 and 5):

3 days after permanent discontinuation of TAF or 30 days after permanent discontinuation of GS-9992, whichever comes last

- For subjects treated with TAF only (ie, Group 2):

3 days after permanent discontinuation of TAF

- Subjects treated with GS-9992 and commercially available NUC(s) (ie, Group 4) are not included in treatment-emergent **Analysis for 48 Week Regimen**.

If the relevant baseline laboratory value is missing, any abnormality of at least Grade 1 observed within the time frame specified above will be considered treatment-emergent.

### 7.2.3.2. Laboratory Abnormalities during TFFU Period

Laboratory abnormalities during TFFU Period are defined as values that increase at least 1 toxicity grade from TFFU baseline at any post treatment time point, up to the end of the study.

### 7.2.3.3. Summaries of Laboratory Abnormalities

Laboratory data that are categorical will be summarized using the number and percentage of subjects in the study with the given response at baseline and each scheduled postbaseline visit for treatment emergent laboratory abnormalities. Laboratory abnormalities during TFFU period will be summarized using the number and percentage of subjects in the study with the given response at TFFU baseline and each scheduled post treatment visit.

3 sets of summaries will be generated: (1) all TE laboratory abnormalities for 12 Week Regimen (2) all TE laboratory abnormalities for 48 Week Regimen for Groups 1-3, 5. (3) all laboratory abnormalities during TFFU after Week 48 for subjects in the TFFU Analysis Set will be listed, and summary tables will be presented using the TFFU Analysis Set as appropriate.

The following summaries (number and percentage of subjects) for laboratory abnormalities will be provided by lab test and by treatment group; subjects will be categorized according to the most severe postbaseline or post TFFU baseline abnormality grade for a given lab test:

- Graded laboratory abnormalities
- Grade 3 or 4 laboratory abnormalities

For all summaries of laboratory abnormalities, the denominator is the number of subjects with nonmissing postbaseline or post TFFU baseline values. A by-subject listing of Grade 3 or 4 laboratory abnormalities, and all graded laboratory abnormalities will be provided by subject ID number and visit in chronological order. This listing will include all test results that were collected throughout the study for the lab test of interest, with all applicable severity grades or abnormal flags displayed.

### 7.2.4. Liver-related Laboratory Evaluations

Liver-related abnormalities after initial study drug dosing will be examined and summarized using the number and percentage of subjects who were reported to have the following laboratory test values for any postbaseline or post TFFU baseline measurements (based on central lab normal range):

1)  $ALT > 1.5 \times \text{nadir}$  and one of the following:

$$ALT \geq 2 \times \text{baseline}$$

$$ALT \geq 10 \times \text{ULN}$$

$$ALT \geq 3 \times \text{ULN and total bilirubin} \geq 2 \times \text{ULN}$$

$$ALT \geq 3 \times \text{ULN and INR} \geq 1.7$$

ALT flare, AASLD Hepatitis flare and ALT elevation will also be summarized using the number and percentage of subjects for any postbaseline or post TFFU baseline measurements as follows (based on both central lab and AASLD normal range):

- ALT flare:  $ALT > 2 \times \text{baseline}$  and  $\geq 5 \times \text{ULN}$
- AASLD Hepatitis flare:  $ALT \geq 3 \times \text{baseline}$  and  $> 100 \text{ U/L}$

2) ALT elevation:  $ALT > 1.5 \times \text{nadir}$  and one of the following:

$ALT \geq 2 \times \text{baseline}$

$ALT \geq 2.5 \times \text{ULN}$  and  $< 5 \times \text{ULN}$

$ALT \geq 5 \times \text{ULN}$  and  $< 10 \times \text{ULN}$

$ALT \geq 10 \times \text{ULN}$

2 sets of summaries will be generated: (1) all liver-related TE laboratory abnormalities and ALT flare/elevation for Week 48 Regimen. (2) all liver-related laboratory abnormalities and ALT flare/elevation during TFFU will be listed, and summary tables will be presented using the TFFU Analysis Set as appropriate.

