### Preliminary Safety

In the Ph 2 study (SBP-9200-HBV-201 [ACHIEVE]) in CHB patients at doses between 25 and 200 mg dosed daily for 12 weeks, all TEAEs were mild to moderate, and the majority were judged as unrelated to study drug administration by the investigator. There were no flu-like events, IFN-like side effects or non-specific immune side effects. At 200 mg there was a single SAE of hospitalization for knee pain which was considered unrelated by the investigator. Three placebo and 6 active patients had ALT flares as defined by elevation of ALT >5 X ULN or 2X nadir, which were considered AEs of special interest. ALT flare was the only Grade 3 laboratory abnormality noted with the exception of one subject who had a Grade 3 triglyceride elevation, which was not confirmed with repeat testing. No ALT flare was associated with a significant increase in bilirubin or INR or a decrease in albumen. No subjects with ALT flare met Hy's law defined as ALT >3xULN AND total bilirubin >2xULN. In the active arm, flares were associated with a reduction in HBV DNA and were considered immune flares. One patient who's ALT went above 10X ULN had inarigivir dosing discontinued at Week 4, with a switch to tenofovir disoproxil fumarate as per protocol. In 2 placebo patients, one ALT flare was secondary to a reversion from HBeAg negative to positive with an increase in HBV DNA by 1 log10 and the second flare was consistent with natural fluctuations of ALT in HBV patients. There were no other Grade 3 or 4 changes in hematology or biochemistry at the time of the flares. Additional data per Cohort are provided below

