### 4.3. Groups 1-3 and 5 Exclusion Criteria

Subjects who meet *any* of the following exclusion criteria are not to be enrolled in this study:

- 1) Pregnant women, women who are breastfeeding or who believe they may wish to become pregnant during the course of the study.
- 2) Co-infection with HCV, HIV, or HDV.
- 3) Extensive bridging fibrosis or cirrhosis as defined clinically, by imaging or by the following:
  - a) Metavir  $\geq 3$  or Ishak fibrosis score  $\geq 4$  by a liver biopsy within 5 years of screening, or, in the absence of an appropriate liver biopsy, either:
  - b) Screening FibroTest score of  $> 0.48$  and APRI  $> 1$ , or
  - c) Historic FibroScan with a result  $> 9$  kPa within  $\leq 6$  months of screening (if available)

If liver biopsy is available, the liver biopsy result supersedes (b) and/or (c, if available)

If an appropriate liver biopsy is not available, fibrosis will be evaluated by (b) and/or (c, if available). In the event of discordance between (b) and (c), the FibroScan results will take precedence.

- 4) Evidence of hepatocellular carcinoma on imaging (e.g., ultrasound, CT scan, or MRI) performed within 3 months prior to the Baseline visit.
- 5) Any history of, or current evidence of, clinical hepatic decompensation (e.g., ascites, encephalopathy or variceal hemorrhage).
- 6) Abnormal hematological and biochemical parameters at Screening, including:
  - Hemoglobin  $< 12$  g/dL for males and  $< 11$  g/dL for females
  - Absolute neutrophil count  $< 1000$  cells/mm^3
  - White blood cell count  $< 2500$  cell/uL
  - Platelets  $< 100,000$ /mm^3
  - AST or ALT  $> 5 \times$  ULN
  - Total Bilirubin  $> 2.5 \times$  ULN
  - Albumin  $< 3.5$  g/dL
  - INR  $> 1.5 \times$  ULN (unless stable on anticoagulant regimen)
  - Creatinine clearance  $< 50$  mL/min

- 7) Received solid organ or bone marrow transplant.
- 8) Significant immunodeficiency disorder, autoimmune, cardiovascular, pulmonary, or neurological disease in the opinion of the investigator.
- 9) Chronic liver disease of a non-HBV etiology (e.g., hemochromatosis, Wilson's disease, alpha-1 antitrypsin deficiency, cholangitis, steatohepatitis).
- 10) Malignancy within the 5 years prior to screening, with the exception of specific cancers that are cured by surgical resection (basal cell skin cancer, etc.). Subjects under evaluation for possible malignancy are not eligible.

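### SAP 7.2.4 counts the combined ALT-with-bilirubin and ALT-with-INR patterns only when ALT also exceeds 1.5 times an undefined nadir, so some subjects with persistently high ALT drop out of the combined count

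*SAP*

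**What the plan says.** SAP 7.2.4 introduces its liver summary with "Liver-related abnormalities after initial study drug dosing will be examined and summarized using the number and percentage of subjects who were reported to have" certain values at any post-baseline or post-TFFU-baseline measurement, using the central laboratory range. List 1 opens with "ALT > 1.5 \times \text{nadir", and a subject must meet that condition plus one of four criteria. Two of the four are ALT alone (at least 2 x baseline, at least 10 x ULN). The other two are the combined patterns: "ALT \geq 3 \times \text{ULN and total bilirubin} \geq 2 \times \text{ULN" and "ALT \geq 3 \times \text{ULN and INR} \geq 1.7". The section's other definitions (ALT flare, AASLD hepatitis flare, ALT elevation) use ALT only. No table visible in the SAP counts either pair without the nadir condition, and nadir is not defined.

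Protocol 1.2.2, reporting the ACHIEVE study, gives a two-part definition with no nadir condition: "Hy's law defined as ALT >3xULN AND total bilirubin >2xULN".

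Protocol 4.3 (criterion 6, "Abnormal hematological and biochemical parameters at Screening, including") excludes viremic subjects with "AST or ALT $> 5 \times$ ULN" or total bilirubin above 2.5 x ULN. Values up to those limits are therefore allowed at screening.

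**The concern.** A combined ALT and bilirubin count is meant to show whether liver enzymes and liver function were abnormal together in the same subject. Requiring a fresh relative rise in ALT makes that count depend on where the subject's ALT started. In a population that must have raised ALT to enter, a subject can hold ALT well above 3 x ULN, develop a raised bilirubin, and miss the row because ALT did not rise by more than half.

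Safety and tolerability over 12 weeks is a primary objective (Protocol 2), and the Group 5 dose rationale (Protocol 1.4.1) names the liver as the only target organ in the pre-clinical toxicology. Groups have about 10 to 30 viremic subjects, so a single case matters to the summary. A zero in the gated row could be set beside the ACHIEVE statement as though both used the same definition.

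**Working it through.** The plan states no figure to reproduce. The check applies the 7.2.4 rule directly, with ALT and bilirubin in multiples of ULN.

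**Inputs.** Gate: ALT > 1.5 x nadir. Pair: ALT >= 3 and bilirubin >= 2 (SAP 7.2.4). Screening ceilings: ALT 5, bilirubin 2.5 (Protocol 4.2, 4.3). Grades (Protocol Appendix 3): ALT Grade 2 is >2.5 to 5 and Grade 3 is >5 to 10; bilirubin Grade 2 is >1.5 to 2.5 and Grade 3 is >2.5 to 5. Treatment-emergent means a rise of at least one grade from baseline, with no nadir condition (SAP 7.2.3.1).

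**Step 1: the uncounted range.** A pair is missed when ALT >= 3 but ALT <= 1.5 x nadir. With nadir as the lowest value so far, the range runs from max(3, nadir) to 1.5 x nadir.

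- Nadir below 2: 1.5 x nadir is below 3, so nothing is missed.
- Nadir 2: 1.5 x 2 = 3.0, so only ALT of exactly 3.0.
- Nadir 2.5: 3 to 3.75.
- Nadir 3: 3 to 4.5.
- Nadir 4: 4 to 6.
- Nadir 5 (the screening ceiling): 5 to 7.5.

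**Step 2: one subject through every 7.2.4 row.** Take baseline and nadir ALT 4, rising to 5.5, with bilirubin 1 rising to 3. The ratio is 5.5/4 = 1.375, below 1.5, so all of list 1 and the ALT elevation list fail at the gate. ALT flare needs more than 2 x 4 = 8, and AASLD flare needs at least 3 x 4 = 12; both fail. The subject is in no 7.2.4 row.

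**Step 3: the same subject in SAP 7.2.3.** ALT goes from Grade 2 to Grade 3 and bilirubin from Grade 0 to Grade 3. Both are treatment-emergent, both enter the Grade 3 or 4 table under their own test, and both are listed by subject. The pairing is not tabulated.

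**Step 4: the meaning of nadir.** Five illustrative courses (assumed, not data):

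| Course | ALT | Bilirubin | Gated, lowest so far | Gated, lowest in whole study | Ungated | Bilirubin grades risen |
|---|---|---|---|---|---|---|
| a | flat at 4 | 0.8 to 3.0 | no | no | yes | 3 |
| b | 5 falling to 3 | 0.8 to 2.6 | no | no | yes | 3 |
| c | flat at 4 | 2.0 to 2.5 | no | no | yes | 0 |
| d | 4 at event, later 1 | 0.8 to 2.3 | no | yes | yes | 2 |
| e | 4 to 2, back to 4 | 0.8 to 3.0 | yes | yes | yes | 3 |

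The gated rule counts 1 of 5 on the first reading and 2 of 5 on the second; the ungated rule counts 5 of 5. Leaving baseline out of the lowest value so far changes nothing here. Course d turns on the definition alone. The Step 2 subject does too: under the whole-study reading, a later ALT below 5.5/1.5 = 3.67 would bring the event in. Course c shows no grade rise, so it reaches only the listings.

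**The case against.** The strongest reply is that the liver signal is not hidden. As Step 3 shows, the graded tables carry no nadir condition, and the by-subject listings let a reader put ALT and bilirubin together by hand. A reader might infer from 7.2.4 that such a subject is counted nowhere. The documents do not support that: only a subject such as course c, already Grade 2 for bilirubin at baseline and not rising a grade, escapes both sets of tables, and that subject is still listed. This stands, and it limits the point to the combined count.

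Second, a relative-rise condition is reasonable when raised ALT is an entry requirement, and Protocol Table 7-1 also ties hepatic toxicity to a multiple of nadir. That justifies keeping the gated rows. But Table 7-1 guides patient management and is not a count. If the gate is meant to remove subjects abnormal at entry, the SAP does not say so, and it does that imperfectly. A subject entering at ALT 3.2 and bilirubin 2.2 x ULN would be counted after a rise in ALT of more than 1.5-fold with no change in bilirubin.

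Third, the ACHIEVE sentence reads "No subjects with ALT flare met Hy's law defined as ALT >3xULN AND total bilirubin >2xULN", so that result is itself confined to subjects with a flare, and the SAP never labels its row Hy's law. Both are correct. Protocol 1.4.1 does, however, say more broadly that no subject met Hy's law, and the two-part definition itself has no nadir condition. The mismatch in definition remains.

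**Conclusion.** The point holds as a gap in the combined count for viremic subjects (Groups 1-3 and 5). Under the lowest-so-far reading, pairs are missed once nadir reaches 2 x ULN, and the range widens to 5 to 7.5 x ULN at nadir 5. Under the whole-study reading the gap is narrower, because a later fall in ALT opens the gate. Courses in which ALT stays at or above 3 x ULN throughout without a 1.5-fold rise are missed on every reading tried.

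The documents do not allow a count of affected subjects, and few are expected. A case needs bilirubin of at least 2 x ULN as well, and Grade 3 or 4 bilirubin occurred in 0.3% (3 subjects) on TAF in the Phase 3 studies (Protocol 1.3.2); that figure does not cover GS-9992. A reader might infer from the Phase 3 median ALT values of 67 and 85 U/L that a large share of viremic subjects is exposed. That does not follow. If ULN is 35 to 45 U/L (an assumption), the medians are 67/45 = 1.5 to 85/35 = 2.4 x ULN, whereas nadir 3 means 105 to 135 U/L, above both.

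This is a modest reporting defect in a primary safety summary, worth correcting because the correction is cheap.

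**What to change.** In SAP 7.2.4:

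- Define nadir, stating whether it is the lowest value so far or over the whole study, and whether baseline is included.
- Keep the gated rows unchanged.
- Add two ungated rows: ALT at least 3 x ULN with total bilirubin at least 2 x ULN, and ALT at least 3 x ULN with INR at least 1.7. Require both values from the same sample, because SAP 3.8.3 takes the largest ALT in a window but, for other continuous tests, the value nearest the nominal day.
- Show each row separately for subjects who did and did not meet the pattern at baseline. Do not exclude the former, since a subject who meets it at entry may still worsen.
- Add a by-subject listing of ALT, bilirubin and INR for everyone counted.

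No new data are needed. After Day 1 the protocol schedules coagulation only at Week 12 (6.3), with INR also at ALT confirmation visits (7.6), so the INR row will rest on few samples and a footnote should say so. The cost is a few table rows and possibly a slightly higher count that includes subjects whose values were raised at entry; the baseline split makes that visible.

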## 2. OBJECTIVES

The primary objectives of this study are:

- To evaluate the safety and tolerability of the 12 week treatment regimens of GS-9992 plus TAF or commercially available NUC

- **Groups 1-3 and 5**

To evaluate the antiviral activity of 12 weeks of GS-9992 plus TAF versus TAF alone in viremic CHB subjects as measured by the proportion of subjects with  $\geq 0.5 \log_{10}$  IU/mL decline from Baseline at Week 12 in circulating serum HBV surface antigen (HBsAg)

- **Group 4**

To evaluate the antiviral activity of 12 weeks of GS-9992 with commercially available NUC(s) in virally suppressed CHB subjects as measured by the proportion of subjects with  $\geq 0.5 \log_{10}$  IU/mL decline from Baseline at Week 12 in circulating serum HBV surface antigen (HBsAg)

The secondary objectives of this study are:

- **Groups 1-3 and 5**

- To evaluate the safety and tolerability of the 48 week treatment regimens as assessed by review of the accumulated safety data
- To evaluate the antiviral activity of 12 weeks of GS-9992 plus TAF versus TAF alone in CHB subjects as measured by the proportion of subjects with  $\geq 1 \log_{10}$  IU/mL decline from Baseline at Week 12 in circulating HBsAg
- To evaluate the proportion of HBeAg-positive CHB subjects who achieve HBeAg loss and seroconversion during 12 weeks of GS-9992 plus TAF versus TAF alone and after GS-9992 discontinuation through 48 weeks
- To evaluate the proportion of CHB subjects who achieve HBsAg loss during 12 weeks of GS-9992 plus TAF versus TAF alone and after GS-9992 discontinuation through 48 weeks
- To evaluate the incidence of drug resistance mutations during 48 weeks of treatment
- To characterize steady-state pharmacokinetics of study drugs
- To evaluate the change from Baseline in HBV DNA and quantitative HBsAg in CHB subjects during 12 weeks of GS-9992 plus TAF versus TAF alone and after GS-9992 discontinuation through 48 weeks

- **Group 4**
- To evaluate the proportion of subjects experiencing HBV virologic breakthrough (2 consecutive visits of HBV DNA  $\geq$  69 IU/mL) during 12 weeks of GS-9992 treatment
- To evaluate the antiviral activity of 12 weeks of GS-9992 in CHB subjects as measured by the proportion of subjects with  $\geq 1$  log10 IU/mL decline from Baseline at Week 12 in circulating HBsAg

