## **8.6. Safety Analysis**

Safety will be evaluated by assessment of clinical laboratory tests and adverse events. Primary safety analysis will be evaluated through four weeks after last dose of GS-9992.

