Hypouricemia Adult and Pediatric ≥ 1 year	1.5 mg/dL to < LLN 87 μmol/L to < LLN N/A	1.0 to < 1.5 mg/dL 57 to < 87 μmol/L 1.0 mg/dl to <LLN- 57 μmol to <LLN	0.5 to < 1.0 mg/dL 27 to < 57 μmol/L 0.5 to < 1.0 mg/dL 27 to < 57 μmol/L	< 0.5 mg/dL < 27 μmol/L < 0.5 mg/dL < 27 μmol/L
Creatinine**	> 1.50 to 2.00 mg/dL > 133 to 177 μmol/L	> 2.00 to 3.00 mg/dL > 177 to 265 μmol/L	> 3.00 to 6.00 mg/dL > 265 to 530 μmol/L	> 6.00 mg/dL > 530 μmol/L
Bicarbonate Adult and Pediatric ≥ 4 Years	16.0 mEq/L to < LLN 16.0 mmol/L to < LLN	11.0 to < 16.0 mEq/L 11.0 to < 16.0 mmol/L	8.0 to < 11.0 mEq/L 8.0 to < 11.0 mmol/L	< 8.0 mEq/L < 8.0 mmol/L
Pediatric < 4 Years	NA	11.0 mEq/L to <LLN 11.0 mmol/L to <LLN	8.0 to < 11.0 mEq/L 8.0 to < 11.0 mmol/L	< 8.0 mEq/L < 8.0 mmol/L

CHEMISTRY				
	Grade 1	Grade 2	Grade 3	Grade 4
Triglycerides (Fasting)	NA	500 to 750 mg/dL 5.64–8.47 mmol/L	> 750 to 1200 mg/dL > 8.47–13.55 mmol/L	> 1200 mg/dL > 13.55 mmol/L
LDL (Fasting) Adult	130 to 160 mg/dL 3.35 to 4.15 mmol/L	>160 to 190 mg/dL >4.15 to 4.92 mmol/L	> 190 mg/dL >4.92 mmol/L	NA
LDL (Fasting) Pediatric >2 to <18 years	110 to 130 mg/dL 2.84 to 3.37 mmol/L	>130 to 190 mg/dL >3.37 to 4.92 mmol/L	> 190 mg/dL >4.92 mmol/L	NA
Hypercholesterolemia (Fasting)	200 to 239 mg/dL 5.16 to 6.19 mmol/L	> 239 to 300 mg/dL > 6.19 to 7.77 mmol/L	> 300 mg/dL > 7.77 mmol/L	NA
Pediatric < 18 Years	170 to 199 mg/dL 4.39 to 5.15 mmol/L	> 199 to 300 mg/dL > 5.15 to 7.77 mmol/L	> 300 mg/dL > 7.77 mmol/L	NA
Creatine Kinase	3.0 to < 6.0 × ULN	6.0 to < 10.0 × ULN	10.0 to < 20.0 × ULN	≥ 20.0 × ULN

\* Calcium should be corrected for albumin if albumin is < 4.0 g/dL

\*\* An overlap between the Grade 1 scale and the Lab's normal range for creatinine may result for Male subjects >70 yrs. Please follow the Gilead convention of grading any result within the LLN and ULN a 0.

ENZYMES				
	Grade 1	Grade 2	Grade 3	Grade 4
AST (SGOT)	1.25 to 2.50 × ULN	> 2.50 to 5.00 × ULN	> 5.00 to 10.00 × ULN	> 10.00 × ULN
ALT (SGPT)	1.25 to 2.50 × ULN	> 2.50 to 5.00 × ULN	> 5.00 to 10.00 × ULN	> 10.00 × ULN
GGT	1.25 to 2.50 × ULN	> 2.50 to 5.00 × ULN	> 5.00 to 10.00 × ULN	> 10.00 × ULN
Alkaline Phosphatase	1.25 to 2.50 × ULN	> 2.50 to 5.00 × ULN	> 5.00 to 10.00 × ULN	> 10.00 × ULN
Total Amylase	> 1.0 to 1.5 × ULN	> 1.5 to 2.0 × ULN	> 2.0 to 5.0 × ULN	> 5.0 × ULN
Pancreatic Amylase	> 1.0 to 1.5 × ULN	> 1.5 to 2.0 × ULN	> 2.0 to 5.0 × ULN	> 5.0 × ULN

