### **2.2. Final Analysis**

After all subjects have completed the study, outstanding data queries have been resolved or adjudicated as unresolvable, and the data have been cleaned and finalized, the final analysis of the data will be performed. The final analysis consists of three parts: analysis for 12 Week regimen, analysis for 48 Week regimen, and TFFU analysis.

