#### 7.1.6. Summaries of Adverse Events and Deaths

AEs will be summarized based on the Safety Analysis Set.

3 sets of summaries will be generated: (1) all TEAEs for 12 Week Regimen (2) all TEAEs for 48 Week Regimen (Group 1-3, and 5). (3) all AEs during TFFU period (AEs that occur during TFFU after Week 48) will be listed, and summary tables will be presented using the TFFU Analysis Set as appropriate.

A brief, high-level summary of the number and percentage of subjects who experienced at least 1 TEAE in the categories described below will be provided by treatment group. All deaths observed in the study will also be included in this summary.

The number and percentage of subjects who experienced at least 1 TEAE will be provided and summarized by SOC, PT and treatment group:

- TEAEs (with severity)

For the AE categories described below, summaries will be provided by PT and treatment group:

- TEAEs
- TEAEs of Grade 3 or higher
- TE treatment-related AEs
- GS-9992 only TE treatment-related AEs (Group 1, 3-5)
- TE treatment-related AEs of Grade 3 or higher
- TE SAEs
- TE treatment-related SAEs
- TEAEs leading to premature discontinuation of GS-9992
- TEAEs leading to premature discontinuation of TAF
- TEAEs leading to dose modification or temporary interruption of GS-9992
- TEAEs leading to dose modification or temporary interruption of TAF

Multiple events will be counted only once per subject in each summary. Adverse events will be summarized and listed first in alphabetic order by SOC and then by PT in descending order of total frequency within each SOC. For summaries by severity grade, the most severe grade will be used for those AEs that occurred more than once in an individual subject during the study.

In addition to the by-treatment summaries described above, data listings will be provided for the following AEs:

- All AEs, indicating whether the event is treatment-emergent
- All AEs of Grade 3 or higher
- SAEs
- All deaths
- AEs leading to premature discontinuation of any study drug
- AEs leading to dose modification or temporary interruption of any study drug

For subjects in the TFFU Analysis Set, by-subject listings will be provided as follows:

- All AEs
- AEs of Grade 3 or higher
- All SAEs
- All deaths

The listings will indicate whether an event is treatment-emergent, and whether the event occurred during TFFU.

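### SAP 7.2.4 plans no 12 Week Regimen set for the composite liver and ALT flare/elevation criteria, and leaves Group 4's place in the 48-week set unsettled

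*SAP*

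**What the plan says.** SAP 2.2 divides the reporting: "The final analysis consists of three parts: analysis for 12 Week regimen, analysis for 48 Week regimen, and TFFU analysis". SAP 7.1.6 follows that division for adverse events: "3 sets of summaries will be generated: (1) all TEAEs for 12 Week Regimen (2) all TEAEs for 48 Week Regimen", with treatment-free follow-up (TFFU) as the third set. SAP 7.2.3.3 does the same for graded laboratory abnormalities. Both sections limit their 48-week set to Groups 1-3 and 5.

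SAP 7.2.4 departs from the pattern: "2 sets of summaries will be generated: (1) all liver-related TE laboratory abnormalities and ALT flare/elevation for Week 48 Regimen". Its second set is TFFU. It names no groups, and its lead-in admits every measurement after baseline.

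The 12-week window is the primary one. The first primary objective in Protocol Section 2 is "To evaluate the safety and tolerability of the 12 week treatment regimens of GS-9992 plus TAF or commercially available NUC". Protocol 8.6 adds: "Primary safety analysis will be evaluated through four weeks after last dose of GS-9992". SAP 2.1.1 implements this as data through 30 days after the last GS-9992 dose, with a matching period for Group 2. Safety of the 48-week regimens is a secondary objective, listed for Groups 1-3 and 5 only.

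**The concern.** GS-9992 is given only in the first 12 weeks. After that, Groups 1, 3 and 5 take TAF alone and Group 4 stays on its own NUC. The table planned in 7.2.4 would count an ALT flare at Week 4 on GS-9992 and one at Week 40 on TAF alone in the same cell.

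The liver is the organ to watch in this trial. Protocol 1.4.1 describes it as the only target organ in the preclinical toxicology, and Protocol 1.2.2 reports that the previous 12-week GS-9992 trial handled ALT flares as events of special interest. What is at stake is whether the report shows these criteria by group for the period when the drug was taken, as a prespecified table.

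**Working it through.** The plan gives no figure to reproduce. The check sets the sections side by side and adds simple arithmetic for scale.

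**1. Planned sets.**

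| SAP section | Content | 12 Week | 48 Week | TFFU |
|---|---|---|---|---|
| 7.1.6 | Adverse events | yes | Groups 1-3, 5 | yes |
| 7.2.3.3 | Graded laboratory abnormalities | yes | Groups 1-3, 5 | yes |
| 7.2.4 | Composite liver, flare, elevation | no | no groups named | yes |

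Nothing in the SAP explains the empty cell.

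**2. How much of the 48-week window lies outside the 12-week one.** SAP 7.2.3.1 gives the cutoffs. Twelve weeks plus 30 days is 84 + 30 = Day 114. Forty-eight weeks plus 3 days is 336 + 3 = Day 339. Then (339 - 114)/339 = 225/339 = 66%. Day 114 is fixed only for Group 2; the GS-9992 groups are cut 30 days after each subject's own last dose, so for them it is the nominal value for a completer. In draws the share is smaller. Nominal ALT days are 8, 15, 29, 57, 85, 113, 169, 253 and 337, so 3 of 9 fall after Day 114, or 4 if the Week 16 visit (Day 113 ± 3) falls on Day 115 or 116.

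**3. What the 12-week output already covers.** The graded tables include ALT, bilirubin and INR singly, for all five groups. Protocol Appendix 3 sets ALT Grade 3 at "> 5.00 to 10.00 × ULN", with Grade 2 at > 2.50 to 5.00 and Grade 4 at > 10.00 × ULN. These nearly match the 2.5 to < 5, 5 to < 10 and ≥ 10 × ULN bands of 7.2.4 on the central-laboratory range. SAP 7.2.1 gives ALT and its change by group and visit, and SAP 3.8.3 keeps the largest ALT in each postbaseline window.

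**4. What it does not cover.** SAP 7.2.3.1 states: "TE laboratory abnormalities are defined as values that increase at least 1 toxicity grade from baseline at any postbaseline time point". A grade rise is not the same as a 7.2.4 event. Viremic subjects may enter with ALT up to 5 × ULN (Protocol 4.2), so take a baseline of 4.5 × ULN:
- A rise to 5.5 is a treatment-emergent Grade 3, but 5.5/4.5 = 1.2, so it is not a flare (> 2 × baseline and ≥ 5 × ULN).
- A rise to 9.5 is also Grade 3, and 9.5/4.5 = 2.1, so it is a flare.
- A fall followed by a return to 4.5 shows no grade rise. If the nadir was below 4.5/1.5 = 3.0 × ULN, it counts as an ALT elevation in the 2.5 to < 5 band.

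Single-test tables also cannot show ALT with bilirubin, or ALT with INR, in the same subject, and they have no AASLD-range version. INR is scheduled after baseline at Week 12 (Protocol 6.3) and is drawn when an ALT elevation is being confirmed (Protocol 7.6), so the ALT-plus-INR row can have data inside the 12-week window.

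**5. Group 4.** SAP 7.2.3.1 leaves Group 4 out of the treatment-emergent 48-week laboratory analysis. SAP 7.2.4 uses the treatment-emergent label, but names no groups and takes any value after baseline; SAP 2.1.2 defines the 48-week analysis without excluding a group. Three readings are open:
- The exclusion carries over to everything in 7.2.4. Then 20/(30 + 30 + 20 + 30) = 20/110 = 18% of planned GS-9992 recipients have no on-treatment table of these criteria. Those who stop their NUC would still appear under TFFU.
- It carries over only to the liver-related abnormalities, and Group 4 stays in the flare/elevation rows.
- It does not carry over, and Group 4's GS-9992 and NUC-only phases are pooled.

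**The case against.** The best defence is that the window is largely covered already. Early events in Groups 1-3 and 5 are counted in the 48-week table, the single-test and by-visit outputs in step 3 are available by group, and listings show each result. Laboratory abnormalities are usually not recorded as adverse events, but those leading to interruption or discontinuation of drug must be (Protocol 7.5), and these reach the 12-week adverse event tables. The protocol itself asks for no composite liver table, and no hypothesis is tested. All of this stands, and it limits the point to the rows named in step 4.

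Four stronger readings are tempting, and the documents do not support them.
- A reader might infer that the whole primary-window hepatic comparison with Group 2 must be rebuilt from listings. That is true only of the composite, nadir, fold-over-baseline and AASLD-range rows.
- A reader might infer that late events would materially dilute a difference between groups. The documents give no late-event rate under these definitions. Protocol 1.3.2 reports ALT elevations on TAF in 1.8% through Week 48, mostly in the first 8 weeks, under a stricter > 10 × ULN definition.
- A reader might take Group 4's omission as settled. It is one of three readings.
- A reader might see a drug excess in the 6 active and 3 placebo flares of the previous trial. Cohort counts in Protocol 1.2.2, with Cohort 4 only partly reported, give about 16 + 16 + 17 + 12 = 61 active and 4 + 4 + 3 + 3 = 14 placebo subjects, or roughly 10% against 21%. The figures show that flares were monitored, not that the drug caused more of them.

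**Conclusion.** The point holds in limited form. One section of the SAP omits the window that the protocol makes primary for safety and that the SAP's own structure provides elsewhere. Followed exactly, the plan gives no 12-week table of the composite liver, flare and elevation criteria, and it pools GS-9992-phase events with later events on TAF alone (or on a NUC alone, if Group 4 is included). This is a gap within the SAP, not a dropped protocol analysis, and no data are lost.

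The 66% of days and 3 or 4 of 9 draws assume a subject who completes treatment on the nominal schedule. The 18% applies only if the Group 4 exclusion carries over in full. The difference between the protocol's four weeks and the SAP's 30 days is 2 days and does not matter here. The point should be fixed because the fix is cheap and serves the primary safety question; it does not threaten the trial's conclusions.

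**What to change.** In SAP 7.2.4, generate three sets:
1. 12 Week Regimen, Groups 1-5, with the cutoffs already in SAP 7.2.3.1.
2. 48 Week Regimen, Groups 1-3 and 5, matching SAP 7.2.3.1 and 7.2.3.3.
3. TFFU.

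State that Group 4 is in set 1 and, for subjects who stop their NUC, in set 3. Keep the liver criteria as written.

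The cost is one extra run of tables whose criteria and cutoffs already exist, plus a sentence on groups; no new data are needed. The drawback is unequal follow-up for subjects who stop early: the window closes 30 days after GS-9992 in Groups 1, 3, 4 and 5, but 3 days after TAF for a Group 2 subject who stops before Day 114. The 12-week graded laboratory tables already use these same cutoffs, so the new set would be consistent with them.
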